7.5 Analysis of Safety

All analysis of safety will be presented by treatment group and overall for SAF, unless specified otherwise.

7.5.1 Adverse Events

For the purpose of safety assessments in this study, events recorded during the pre-investigational period will be classified as Baseline Signs and Symptoms. All adverse event (AE) recorded on treatment including within 30 days from the last study treatment will be summarized.

The coding dictionary for this study will be MedDRA v18.0. It will be used to summarize AEs by SOC and PT. AEs will be graded using National Cancer Institute's Common Terminology Criteria for AEs (NCI-CTCAE).

An overview table will include the following details by treatment group and overall:

- Number and percentage of subjects with TEAEs,
- Number and percentage of subjects with causally drug-related TEAEs,
- Number and percentage of subjects with serious TEAEs and Astellas upgraded serious TEAE,
- Number and percentage of subjects with serious drug-related TEAEs and Astellas upgraded serious drug-related TEAE,
- Number and percentage of subjects with TEAEs leading to permanent discontinuation of study drug,
- Number and percentage of subjects with drug-related TEAEs leading to permanent discontinuation of study drug,
- Number and percentage of subjects with grade 3 or higher TEAE
- Number and percentage of subjects with TEAEs leading to dose reduction,
- Number and percentage of subjects with drug-related TEAEs leading to dose reduction,
- Number and percentage of subjects with TEAEs leading to drug interruption,
- Number and percentage of subjects with drug-related TEAEs leading to drug interruption, and
- Number of deaths.

The number and percentage of subjects with TEAEs, as classified by SOC and PT will be summarized by treatment group and overall. Summaries will be provided for:

- TEAEs
- Drug-related TEAEs,
- serious TEAEs and Astellas upgraded serious TEAE,
- drug-related serious TEAEs and drug-related Astellas upgraded serious TEAE,
- TEAEs leading to permanent discontinuation of study drug,
- Drug-related TEAEs leading to permanent discontinuation of study drug,
- TEAEs leading to dose reduction,
- Drug-related TEAEs leading to dose reduction,
- TEAEs leading to drug interruption,
- Drug-related TEAEs leading to drug interruption,
- TEAEs excluding serious adverse events that equal to or exceed a threshold of 10% in any dose level, and
- Common TEAEs that equal to or exceed a threshold of 10% in any dose level.
- TEAE with CTCAE Grade 3 or higher

The number and percentage of subjects with TEAEs and TEAEs leading to death, as classified by PT only, will be summarized by treatment group and overall.

AE summary tables will include subject counts as opposed to AE counts. If a subject experiences more than one episode of a particular AE, that subject will be counted only once for that event. If a subject has more than one AE that code to the same preferred term, the subject will be counted only once for that preferred term. Similarly, if a subject has more than one AE within a body system, the subject will be counted only once in that body system.

TEAEs and the number and percentage of subjects with TEAEs, as classified by SOC and PT will also be summarized by NCI-CTCAE severity grade and by relationship to study drug. If an adverse event changes in severity grade or relationship, then the subject will be counted only once with the worst severity grade and highest degree of relationship. The adverse event however will be presented in each category they were classified to. If a subject has an event more than once with missing severity grade/relationship and with non-missing severity grade, then the subject will be counted as the highest non-missing grade. If a subject has an event more than once with missing relationship and with non-missing relationship, then the subject will be counted as missing. Drug-related TEAEs will be presented in a similar way by severity only.

The exposure adjusted subject incidence rates of adverse events may be compared between treatment groups for selected categories of adverse events. The exposure adjusted subject incidence (subjects/subject-year) is defined for any particular adverse event as the number of subjects in a treatment group that experienced the specific event at least once divided by the total amount of time (100 subject-year) the subjects in the treatment group have been exposed

to the study drug. For subjects that experience the event, their exposure time will be calculated as the time between the first dose date up to the initial occurrence of the event. For subjects who do not experience the event, their exposure time will be calculated as the time between the first dose date through 30 days after the last dose date, the date of death, or the end of study date, whichever is earlier. For subjects that experience multiple events, their exposure time will be calculated up to the onset of the first event.

The number and percentage of subjects with treatment-emergent adverse events of interest, as classified by SOC and PT will also be summarized by treatment group and overall. The list of adverse events of interest to be summarized may change during the course of the study due to ongoing pharmacovigilance. It will be finalized before the database hard lock.

All AEs, deaths, SAEs and withdrawals due to adverse events will be displayed in listings.

All AEs occurring during or after the subject has discontinued the study are to be followed up until resolved or judged to be no longer clinically significant, or until they become chronic to the extent that they can be fully characterized.

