7.10 Handling of Missing Data, Outliers, Visit Windows, and Other Information

As a general principle, no imputation of missing data will be done. Exceptions are the start and stop dates of AEs and concomitant medication. The imputed dates will be used to allocate the concomitant medication and AEs to a treatment group, in addition to determining whether an AE is/is not treatment-emergent. Listings of the AEs and concomitant medications will present the actual partial dates; imputed dates will not be shown.

Subjects with missing overall response assessment will be regarded as nonresponders in ORR analysis.

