6.2 Safety Variables

Safety endpoints such as AEs, laboratory tests, vital signs, ECGs and ECOG performance status are secondary endpoints of the study.

Safety will be assessed by evaluation of the following variables:

- Treatment-emergent adverse events (TEAEs; frequency, severity, seriousness, and relationship to study drug).
 - TEAE is defined as an adverse event observed after starting administration of the study drug. If the adverse event occurs on Day 1 and the onset check box is marked "Onset after first dose of study drug" or the onset check box is left blank, then the adverse event will be considered treatment emergent. If the adverse event occurs on Day 1 and the onset check box is marked "Onset before first dose of study drug", then the adverse event will not be considered treatment emergent. If a subject experiences an event both during the pre-

investigational period and during the investigational period, the event will be considered as TEAE only if it has worsened in severity (i.e. it is reported with a new start date). All adverse events collected that begin within 30 days after taking the last dose of study drug will also be counted as TEAE. Any AEs with onset dates completely missing will be considered TEAEs in summaries. AEs with partially missing onset dates will be assumed TEAEs unless the available portion of the date indicates that the onset was strictly before start of study medication.

- A drug-related TEAE is defined as any TEAE with at least possible relationship (possibly or probably related) to study treatment as assessed by the investigator or with missing assessment of the causal relationship
- Serious adverse events (SAEs) include adverse events that are flagged as serious by the investigator on eCRF, or upgraded by the Sponsor based on review of the Sponsor's list of Always Serious term.
- Clinical laboratory variables

Below is a table of the laboratory tests that will be performed during the conduct of the study. Refer to the Schedule of Assessments for study visit collection dates.

Additional laboratory tests should be performed according to institutional standard of care. Clinical significance of out-of-range laboratory findings is to be determined and documented by the investigator or delegated sub-investigator who is a qualified physician.

Table 3 Laboratory Assessments

Panel/Assessment	Parameters to be analyzed	NCI-CTCAE
		Grading
		(Hyper/Hypo)
Hematology	Hematocrit (Hct)	N/A
	Hemoglobin (Hgb)	Both

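### In the by-relationship adverse event count, one unrated record moves a subject out of the Possible or Probable row and into missing

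*SAP*

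**What the plan says.** SAP 7.5.1 sets out how a subject is placed when an event carries more than one severity grade or causality rating.

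- Where the grade or relationship changes, "the subject will be counted only once with the worst severity grade and highest degree of relationship".
- At event level nothing is collapsed: "The adverse event however will be presented in each category they were classified to".
- Where some grades are missing and others recorded, "then the subject will be counted as the highest non-missing grade".
- Where some relationships are missing and others recorded: "If a subject has an event more than once with missing relationship and with non-missing relationship, then the subject will be counted as missing".
- The drug-related tables do not use the finer split: "Drug-related TEAEs will be presented in a similar way by severity only".

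SAP 6.2 defines a drug-related event as one rated possible or probable, "or with missing assessment of the causal relationship". Protocol 5.5.3 provides three ratings: Not Related, Possible and Probable.

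**The concern.** The paragraph takes the worst case for relationship when ratings differ, and for severity when some grades are missing. For relationship with a missing rating it does neither: the blank record decides the subject's row, whatever the other records say. No reason is given for treating the two scales differently.

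Ranking missing above Not Related is cautious and agrees with SAP 6.2. Ranking it above Possible or Probable adds no caution, because such a subject is already known to have an event the investigator would not rule out as related. It only takes an existing rating out of the subject count.

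What is at stake is the readability of one table. SAP 7.5.1 says adverse event tables count subjects rather than events, so the subject row is the one most readers will use. Protocol 5.5.3 separates Probable from Possible by whether another cause is unlikely and by the course on withdrawal or rechallenge, and a by-relationship table exists to show that separation. Events with several records per subject give the rule more chances to act. Protocol 1.4 names diarrhea, nausea and vomiting among the commonest events on ASP8273, and these can recur.

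**Working it through.** The plan states no figure to reproduce, so the check is a list of cases.

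**Inputs.** The three ratings in Protocol 5.5.3, the counting rules in SAP 7.5.1, and the definition of drug-related in SAP 6.2.

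**Cases.** Take one subject and one event with at least one unrated and at least one rated record. The rated records form a non-empty subset of three ratings, so there are 2³ − 1 = 7 cases. The column for the highest-degree rule is filled only where the recorded ratings differ, since only then is that rule clearly triggered.

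| Case | Ratings present besides missing | Missing rule as written | Highest-degree rule | Order Probable > Possible > missing > Not Related |
|---|---|---|---|---|
| 1 | Not Related | missing | – | missing |
| 2 | Possible | missing | – | Possible |
| 3 | Probable | missing | – | Probable |
| 4 | Not Related, Possible | missing | Possible | Possible |
| 5 | Not Related, Probable | missing | Probable | Probable |
| 6 | Possible, Probable | missing | Probable | Probable |
| 7 | Not Related, Possible, Probable | missing | Probable | Probable |

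**Results.**

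1. As written, 7 of 7 cases go to missing. Six of them (cases 2 to 7) contain a Possible or Probable rating.
2. In 4 of 7 (cases 4 to 7) both relationship rules apply and give different answers. The SAP does not say which prevails.
3. In the other 3 (cases 1 to 3) only the missing rule is clearly triggered.
4. Under SAP 6.2 the subject is drug-related in 7 of 7, because the unrated record alone is enough. This is the same under any ordering.
5. Copying the severity rule exactly (highest recorded rating wins) would give 1 Not Related, 2 Possible and 4 Probable. Case 1 would then sit under Not Related in this table while counting as drug-related elsewhere.
6. The order in the last column gives 4 Probable, 2 Possible and 1 missing, and agrees with SAP 6.2 in every case.

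These are counts of logical cases, not expected frequencies.

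**The case against.** The best defence is that the sentence is a deliberate special case. The highest-degree rule speaks of an event whose rating changes. The later sentence speaks of an event occurring more than once with some ratings absent, and a programmer would normally let the specific rule prevail. Showing missing causality openly, rather than covering it with a rated record, is also a recognisable convention, and Protocol 7.10 says "As a general principle, no imputation of missing data will be done".

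Part of this stands. A reader might infer that the paragraph flatly contradicts itself. It does not in general: the clash is confined to the four cases with differing ratings plus a missing one, and even there the specific rule can be read as an exception. What remains is that the exception departs from the paragraph's own principle without a stated reason. The no-imputation principle does not rescue it, since using a rating the investigator recorded imputes nothing.

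A reader might also infer that the investigator's rating is lost, or that drug-related toxicity is understated. Neither is supported. Each event stays in every category it was given, SAP 7.5.1 lists all adverse events, and missing causality counts as drug-related. Protocol 5.5.3 itself pools Possible and Probable as a relationship that could not be excluded, and no test, threshold or stopping rule uses the finer split.

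Missing causality should also be uncommon by database lock. Protocol 8.1.1 makes sites responsible for complete eCRF data, and Protocol 5.5.5 requires a causality rating for every serious event. That bears on how often the rule acts, not on whether it is right.

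**Conclusion.** The point holds as a minor defect in a counting rule. Followed literally, SAP 7.5.1 places a subject with a documented Possible or Probable record under missing whenever another record of that event is unrated. Each affected subject moves by one row for that event in one descriptive table. Efficacy, type I error and power are untouched.

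The number of subjects affected cannot be derived from the documents. It is tempting to assume that a share m of records is unrated and that a subject has k records, at least one of them rated, and to use 1 − (1 − m)^(k − 1). With k = 4 this gives 1 − 0.99³ = 3.0% for m = 1% and 1 − 0.97³ = 8.7% for m = 3%. The documents do not support that range. Both m and k are assumptions, records are treated as independent, and the formula counts the loss of any rating, including Not Related, where staying under missing is what SAP 6.2 implies. It is therefore not the share of subjects losing a Possible or Probable rating. If every record is rated at lock, the effect is zero.

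**What to change.** Replace the missing-relationship sentence in SAP 7.5.1 with:

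> For subject counts by relationship, a subject with more than one record of an event is counted once, using the order Probable > Possible > missing > Not Related.

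This restores the highest-degree principle, settles which rule prevails when ratings differ and one is missing, and keeps missing plus Not Related under missing, in line with SAP 6.2. Because missing is used only when an unrated record exists, subjects whose records are all rated Not Related stay in that row.

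The cost is one SAP sentence and one line of derivation code. SAP section 1 allows version-controlled revisions until database hard lock.

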7.5.2 Clinical Laboratory Evaluation

The baseline visit is the last measurement taken prior to initial study drug administration.

Selected quantitative clinical laboratory variables, i.e. hematology, biochemistry, coagulation and urinalysis will be summarized using mean, standard deviation, minimum, maximum and median by treatment group at each visit. Additionally, a within-subject change will be calculated as the post-baseline measurement minus the baseline measurement and summarized in the same way. Changes in laboratory values will be summarized for baseline values versus minimum, maximum and last post-baseline values. Plots of median lab values at each scheduled assessment time by treatment group may be provided for each laboratory parameter.

Frequency tabulations of selected qualitative clinical laboratory variables (i.e. urinalysis) will be presented by treatment group at each visit.

Laboratory results will also be graded using NCI-CTCAE, where possible. Parameters that have criteria available for both low and high values, i.e., hypo- and hyper-, will be summarized for both criteria. The same subject can be counted for both values if the subject has different laboratory values meeting each criterion. NCI-CTCAE grade of laboratory evaluations will be summarized by number and percentage of subjects for each visit. Shift tables of NCI-CTCAE grade change from baseline to worst post-baseline grade for selected laboratory parameters will also be presented.

The list of laboratory parameters to be summarized may change during the course of the study due to ongoing pharmacovigilance. It will be finalized before the database hard lock.

Laboratory data will be displayed in listings.

7.5.2.1 Liver Enzymes and Total Bilirubin

The following potentially clinically significant criteria in liver function tests for Alkaline Phosphatase (ALP), Alanine Transaminase (ALT), total bilirubin, Aspartate Transaminase (AST) and their combination are defined. The subject's highest value during the investigational period will be used.

Parameter ALT	Criteria > 3xULN
	> 5xULN
	> 8xULN
AST	> 3xULN
	> 5xULN
	> 8xULN
ALT or AST	> 3xULN
	> 5xULN
	> 8xULN
Total Bilirubin	> 2xULN
ALP	> 1.5xULN
ALT and/or AST AND Total Bilirubin(*)	(ALT and/or AST $> 3xULN$) and total bilirubin $>= 2xULN$

^(*) Combination of values measured within same sample

The number and percentage of subjects with potentially clinically significant values in liver enzymes and total bilirubin during the investigational period will be presented by treatment group.

7.5.3 Vital Signs

The baseline visit is the last measurement taken prior to initial study drug administration.

Vital signs (systolic blood pressure, diastolic blood pressure, pulse rate and body temperature) will be summarized using mean, standard deviation, minimum, maximum and median by treatment group and visit. Additionally, a within-subject change will be calculated per visit as the post-baseline measurement minus the baseline measurement and summarized by treatment group and visit.

7.5.4 Electrocardiograms (ECGs)

Number and percentage of subjects with normal and abnormal results as assessed locally for the overall interpretation will be tabulated by treatment group at each treatment visit and time point.

7.5.5 Pregnancies

A detailed listing of all pregnancies will be provided.

7.5.6 Physical Examinations

A listing of physical examination results will be produced.

7.5.7 ECOG Performance Status

Summary statistics (number and percent of subjects) for each category of the ECOG performance status at each assessment will be provided. The change from baseline to final visit or early termination will also be summarized. Negative change scores indicate an improvement. Positive scores indicate a decline in performance.

Time to deterioration from baseline in ECOG performance status defined as the change in score from 0 to 2 (or worse) or 1 to 2 (or worse) or 2 to 3 (or worse) will also be summarized. The time to deterioration will be calculated in reference to the randomization date.

7.6 Analysis of PK

PK analysis will be conducted on the PKAS.

Plasma concentrations of ASP8273 and its metabolite(s) (if applicable) will be summarized for Arm A (ASP8273 arm) and where appropriate by nominal time points using descriptive statistics, including number of subjects, mean, standard deviation, minimum, median, maximum, geometric mean, and coefficient of variation (CV).

7.7 Analysis of Biomarker

Selected efficacy endpoints will be summarized for the following groups:

- o EGFR mutation detected by local and central assessments
- EGFR mutation detected by central assessment but not local

Additional potential biomarkers that may affect treatment outcome will be explored and analyses details will be defined in a separate biomarker analysis plan.

7.8 Subgroups of Interest

PFS#1 by IRR, OS, DOR and ORR by IRR will be summarized for the subgroups defined on the basis of the categorized variables listed below:

Grouping variable Subgroups
Age group < 65 years

>=65 years - <75 years

>=75 years

Sex Female

Male

Race Asian

Non-Asian

ECOG status at baseline 0 and 1

2

EGFR status Exon 19 Deletion

Exon 21 L858R

TKI chosen Erlotinib

Gefitinib

Additional analyses may be performed to explore treatment outcome between ECOG status at baseline scores 0 and 1. Forest plots for PFS#1 by IRR and OS will be produced to summarized the treatment effect across subgroups. PFS#1 by IRR, OS, DOR and ORR by IRR may also be summarized using three treatment arms (i.e. ASP8273, Erlotinib and Gefitinib).

7.9 Interim Analysis (and Early Discontinuation of the Clinical Study)

An interim futility analysis is planned to occur after 210 PFS events are observed, which is expected to occur approximately 22 months after the first subject is randomized. If the observed HR is less than 1.1, recruitment into the study will continue as planned until 600 subjects are recruited. If the observed HR at the interim is larger than 1.1, recruitment into the study may be stopped at the interim analysis. Further review of the efficacy data, including secondary endpoints, will be performed by the sponsor to determine whether other evidence of clinical benefit justifies reopening enrollment. If the data do not justify reopening enrollment, enrollment may remain closed, and a decision will be made by the sponsor regarding termination of the study. If the futility analysis takes place after enrollment is completed and the HR is greater than 1.1, subjects who in the opinion of the investigator and the sponsor's Medical Monitor are continuing to derive benefit may continue to receive study drug as randomized. As the interim analysis is for futility only, type I error at final analysis will not be affected.

The interim analysis will be conducted by the IDMC. In addition safety data reviews during the trial will be conducted by the IDMC on a periodic basis. For example, the IDMC will review safety data after the first 50 patients have been randomized plus 3 months. The full procedures for IDMC safety review will be described in a separate IDMC charter.

7.10 Handling of Missing Data, Outliers, Visit Windows, and Other Information

7.10.1 Missing Data

Every effort will be made to resolve missing or incomplete dates for adverse events and concomitant medications. If a partial date cannot be resolved, the most conservative imputation methods will be used to complete the missing information.

Missing or partial start and stop dates of adverse events, non-medication therapy and concomitant medication will be imputed using the following algorithm:

- Imputation rules for partial or missing stop dates:
 - o If the month and year are present, then impute as the last day of that month.
 - o If only the year is present, impute as December 31 of that year.
 - o If the stop date is entirely missing, assume the event or medication is ongoing.
- Imputation rules for partial or missing start dates:

		Stop Date						
		Complete: yyyymmdd		Partial:	Partial: yyyymm		Partial: yyyy	
Star	t Date	< 1 st dose	≥ 1 st dose	< 1 st dose yyyymm	≥ 1 st dose yyyymm	< 1 st dose	≥ 1 st dose yyyy	
Partial:	= 1 st dose yyyymm	2	1	2	1	n/a	1	1
уууутт	≠ 1 st dose yyyymm	2	2	2	2	2	2	2
Partial:	$= 1^{st} dose$ $yyyy$	3	1	3	1	n/a	1	1
уууу	$\neq 1^{st}$ dose $yyyy$	3	3	3	3	3	3	3
Mi	ssing	4	1	4	1	4	1	1

^{1 =} Impute as the date of first dose; 2 = Impute as the first of the month; 3 = Impute as January 1 of the year;

The imputed dates will be used to determine whether an AE is/is not treatment emergent. Listings of AEs, non-medication therapy and concomitant medications will present the actual partial dates; imputed dates will not be shown.

For secondary endpoint OS, missing or incomplete death date will be imputed as the earliest feasible date on or after the date last known to be alive as the examples shown in the table below.

^{4 =} Impute as January 1 of the stop year

Sponsor: Astellas Pharma Global Development, Inc.

ISN/Protocol 8273-CL-0302

Incomplete Date of Death (YYYY MMM DD)	Date Last Know to be Alive (YYYY MMM DD)	Imputed Date of Death (YYYY MMM DD)
2005 APR ??	2005 MAR 31	2005 APR 01
2005 ??? 13	2005 MAR 31	2005 APR 13
2005 ??? ??	2005 MAR 31	2005 MAR 31
????? APR ??	2005 MAR 31	2005 APR 01
????? APR 13	2005 MAR 31	2005 APR 13
???? ??? ??	2005 MAR 31	2005 MAR 31

